
Safety Outcome Measures:
	
Adverse events (AEs), AEs of special interest (AE-SI), clinical laboratory evaluations, vital signs, physical examinations including injection site evaluation and concomitant medication/treatment review.
 
Ophthalmic complications are well known to complicated severe AD with incidence rates of 32-56% (2, 3, 4, 5, 6, 7). Nonetheless, conjunctivitis has been a subject of interest in the dupilumab experience. Due to this experience, conjunctivitis and other ophthalmic events should be evaluated by an ophthalmologist and appropriate treatment rendered until resolution.

Mandatory Early Termination from Study Treatment
	
Using CTCAE Version 5.0 (Common Terminology Criteria for Adverse Events; https://ctep.cancer.gov/protocoldevelopment/electronic_applications/docs/CTCAE_v5_Quick_Reference_5x7.pdf), subjects who develop any related grade 2 or higher cardiovascular or respiratory treatment-emergent adverse events

	
(TEAE) or any related grade 3 or higher TEAE involving other organ systems must be discontinued from further study treatment dosing and monitored until resolution or stabilization.

Concomitant Medications:
	
The following treatments are not permitted, and any use must result in study treatment discontinuation if started after receiving the first dose of study treatment on D1:
 
 • Dupilumab or any antibody against IL-4Rα or IL-13 • Topical agents such as phosphodiesterase (PDE) inhibitors, Janus kinase (JAK) inhibitors, tacrolimus or pimecrolimus • Systemic treatment with steroids or other immunosuppressive and/or immunomodulating substances, e.g., cyclosporine, mycophenolate-mofetil, azathioprine, methotrexate or oral Janus kinase (JAK) inhibitors • Cell depleting agents, e.g. rituximab or treatment with other biologic therapeutics • TCM or Herbal medications for AD treatment including topical preparations 
Use of the following is also prohibited during the study participation:
 
 • Allergen immunotherapy • Live (attenuated vaccine) • Phototherapy (narrow band ultraviolet B [NBUVB], ultraviolet B [UVB], ultraviolet A1 [UVA1], psoralen + ultraviolet A [PUVA]), tanning beds, or any other light emitting device (LED) • More than 2 bleach baths per week

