11.1.5. AE of Special Interest

An AESI is an AE (serious or nonserious) of scientific and medical concern specific to the

sponsor's product or program, for which ongoing monitoring and immediate notification by the Investigator to the sponsor is required. Such events may require further investigation in order to characterize and understand them. Adverse events of special interest may be added or removed during a study by protocol amendment.

Ophthalmic complications are well known to complicated severe AD with incidence rates of 32-56% (2, 3, 6). Nonetheless, conjunctivitis and keratitis have been subjects of interest in the dupilumab experience. In Akinlade, the authors reported that in the combined dupilumab AD experience (n=1047) there were a total of 90 (8.6%) of patients reporting at least one AE of "conjunctivitis" while those patients in the placebo group (n=517) reported 11 (2.1%) such events. Conjunctivitis AEs were mostly mild to moderate in severity with severe events reported in $\leq 0.5\%$ of the dupilumab combined group vs. $\leq 0.3\%$ of the placebo group. Two patients in the dupilumab group permanently discontinued treatment due to a conjunctivitis event. Onset typically occurred during weeks 4-8 and events became less common with long-term treatment. Conjunctivitis was more common in those patients with severe AD at baseline, those with a prior history of conjunctivitis and those with higher baseline levels of TARC and IgE. Pooled dupilumab data suggested that conjunctivitis incidence may decrease with higher trough concentrations of dupilumab.

Due to the dupilumab experience, conjunctivitis, keratitis and other ophthalmic events will be considered AEs of special interest and should be evaluated by an ophthalmologist and appropriate treatment rendered until resolution.

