All AEs will be coded using MedDRA version 24.0 or higher. A treatment-emergent AE (TEAE) is defined as any AE that occurs or worsens after initiation of study treatment.

The duration in days of each AE will be calculated as (resolution date of AE – onset date of AE + 1). For the determination of TEAEs and calculation of durations for AD flares, the following rules regarding partial dates will be applied:

- If only the day is missing for a start date, the 1st of the month will be imputed. If the new estimated date falls before the date of first dose, while the known month and year match the month and year of the first dose, the date of first dose will be used as the new estimated date. The AE will be considered as a TEAE.
- If only the day is missing for an end date, the last day of the month will be imputed. If the new estimated date falls after the date of last study visit, the date of last study visit will be used as the new estimated date.
- If both the day and the month are missing for a start date or end date, no imputation will be used, and the duration will not be calculated. However, if the year of start is the same or greater than the year of the first dose date, the AE will be considered as treatment emergent.

- If the start date or end date is completely missing, duration will not be calculated. However, an event with completely missing start date will be considered as treatment emergent.

An overall summary of AEs will be presented by treatment and overall. The summary will include the total number of events, frequency counts and percentages with:

- All AEs
- TEAEs
- Treatment-emergent Serious Adverse Events (SAEs)
- Treatment-related TEAEs
- Treatment-related treatment-emergent SAEs
- TEAEs leading to study drug discontinuation
- Injection site reactions
- AEs of Special Interest (AESIs): conjunctivitis, keratitis and other ophthalmic events evaluated by an ophthalmologist.

Summaries of the incidence of TEAEs will be displayed by treatment according to the following:

- All TEAEs by SOC in descending order of frequency (in the sequence of all subjects, all active treatments, CBP-201 3000 mg [300 mg Q2W] group) and PT in the same order of frequency
- All TEAEs by SOC, PT, and maximum severity (1 mild, 2 moderate, 3 severe, 4 life-threatening, 5 death)
- All TEAEs by SOC, PT, and maximum causality (not related, related) to study treatment
- All serious TEAEs by SOC and PT
- All AESI by SOC and PT

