For these summaries, subjects with multiple AEs will be counted only once per SOC and PT.

All AEs will be presented in a by-treatment, and by-subject listing, detailing the verbatim term given by the investigator, the PT, SOC, onset date, end date, CTCAE grade, outcome, relationship to study treatment, action taken with study drug, other action taken, seriousness and criteria for seriousness. SAEs and AEs leading to study treatment discontinuation, and AESI will also be presented in a separate listing.

COVID-19 related adverse events may also be summarized separately if deemed necessary.

C. Clinical Laboratory Results

For continuous laboratory parameters, descriptive statistics will be presented for the value at each assessment time and for the changes from baseline labs by treatment group.

Additionally, clinical laboratory parameters will be categorized as low, normal, or high according to laboratory range specifications and the number and percentage of subjects in each category will be presented in shift tables.

Laboratory values that are outside the normal range will also be flagged in the data listings, along with corresponding normal ranges.

D. Vital Signs

Vital signs including sitting blood pressure (systolic and diastolic), heart rate, body temperature and respiratory rate will be presented in a by-subject listing by visit. Descriptive summaries of actual values and changes from Baseline will be calculated for vital signs by treatment group.

E. Electrocardiogram (ECG)

Descriptive statistics will be used to summarize ECG results (actual values and changes from Baseline) at Screening, Baseline (Day 1), and Day 169/Week 24. The incidence of abnormal ECG interpretation will be summarized.

All results will also present in a by-subject listing and abnormal ECG findings will be flagged.

F. Physical Examination

The frequency of subjects with abnormal evaluations of body system findings for physical examinations will be summarized by visit and treatment group. Abnormal physical examination findings will also be presented in a by-subject listing.

Any new findings of Clinically significant abnormalities in physical exam will be recorded as AEs.

G. Injection Site Assessment

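### Read literally, SAP 9.B makes evaluation by an ophthalmologist part of the AESI definition; protocol 11.1.5 does not, and the difference is undeclared

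*SAP*

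**What the plan says.** Protocol section 11.1.5 sets the definition: "conjunctivitis, keratitis and other ophthalmic events will be considered AEs of special interest and should be evaluated by an ophthalmologist". One clause gives the events their status; a second says what should be done about them. The synopsis, under safety outcome measures, repeats only the instruction: "conjunctivitis and other ophthalmic events should be evaluated by an ophthalmologist". Neither place sets a severity threshold for referral.

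SAP section 9.B lists the categories of the overall adverse event summary. The last is the AESI category, given as "conjunctivitis, keratitis and other ophthalmic events evaluated by an ophthalmologist".

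The same category feeds two further outputs in SAP 9.B: a table described as "All AESI by SOC and PT", and a listing, where the SAP says "AESI will also be presented in a separate listing".

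SAP section 11 gives three departures from the protocol: added Week 20 time points, the order of testing the regimens, and the choice of LOCF as the main imputation with WOCF as sensitivity analysis. None concerns AESIs.

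**The concern.** In the protocol an ocular event is an AESI because of what it is. In the SAP wording, taken at face value, it is an AESI because of what it is and because a specialist saw the subject. Under that rule the AESI counts would measure two things at once: how often ocular events occurred, and how often sites and subjects completed the referral.

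Ophthalmic events are the only AESIs the protocol names, chosen because of experience with another antibody against the same receptor. The AESI row is also the only row of the overview defined to bring these events together, so it is where a reader will look first for the incidence by arm.

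The wording also leaves the programmer to choose. The qualifier may cover all three event types, may cover only the last, or may be shorthand with no intended effect. No term list settles it, so two programmers could build different AESI sets from the same data.

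**Working it through.** The plan gives no figure to reproduce on this point, so the check compares the wording and then adds an illustration of size.

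**1. Status and evaluation**

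| | Protocol 11.1.5 | SAP 9.B, read literally |
|---|---|---|
| Ocular event, evaluated by an ophthalmologist | AESI | AESI |
| Ocular event, not evaluated | AESI | not an AESI |

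The two sets differ only in the second row. Two other statements in protocol 11.1.5 support its broader set. AESIs call for immediate notification of the sponsor, which implies that status attaches when the event is identified. AESIs are also to be added or removed by protocol amendment, so a phrase in the SAP is not the stated route for narrowing the set.

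**2. Which outputs are affected**

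- Affected: the AESI row of the overview, the AESI table by SOC and PT, and the AESI listing.
- Not affected: the tables of all TEAEs by SOC and PT, by maximum severity and by causality. An unevaluated event that is treatment-emergent is counted in each of them.
- Not affected: the general listing, since "All AEs will be presented in a by-treatment, and by-subject listing".
- Not affected: any hypothesis test. Protocol 13.7 and SAP section 9 plan no formal comparison of safety endpoints.

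**3. Whether the literal rule can be applied**

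Protocol 11.1.4 lists the information collected for each adverse event: name, dates, severity, relationship, action taken, outcome and seriousness. Evaluation by an ophthalmologist is not among them, nor is it named among the contents of the SAP's AE listing. The CRF is not part of the documents, so a field may exist. If it does not, the literal rule cannot be derived from the listed items.

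**4. Illustration of size**

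Inputs:
- Conjunctivitis rates quoted in protocol 11.1.5 for another drug: 90/1047 = 8.60% on active, 11/517 = 2.13% on placebo. Both agree with the protocol's rounded 8.6% and 2.1%.
- Planned size from SAP 4.C: 55 per arm, so 3 × 55 = 165 active and 55 placebo.
- Share of events evaluated, r: not in the documents. It is varied here and assumed equal in both groups.

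Formulas: subjects in the AESI row = n × rate × r; difference = (8.60% − 2.13%) × r.

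At r = 100%: 165 × 90/1047 = 14.2 and 55 × 11/517 = 1.2.

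| r | Active (of 165) | Placebo (of 55) | Difference, percentage points |
|---|---|---|---|
| 100% | 14.2 | 1.2 | 6.5 |
| 75% | 10.6 | 0.9 | 4.9 |
| 50% | 7.1 | 0.6 | 3.2 |
| 25% | 3.5 | 0.3 | 1.6 |

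The first line is what the protocol instructs. With r equal in the two groups, the ratio between them is unchanged and the difference shrinks in proportion to r. The tables of all TEAEs are the same on every line.

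**The case against.** The strongest reply is that no redefinition was meant. The SAP phrase follows the protocol sentence closely and may simply condense it. By grammar the qualifier may attach only to the last item, leaving conjunctivitis and keratitis unconditional. The SAP's introduction says it does not restate every protocol definition, and the silence of section 11 fits that account. Sites identify and report AESIs under the protocol in any case. All of this stands as a plausible account of intent. It does not settle how the row will be programmed.

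Second, if every ocular event is evaluated as the protocol says it should be, the two sets are identical. That also stands. But an instruction does not guarantee completion, and the reported incidence should not depend on it.

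Two stronger readings are tempting, and the documents do not support them. A reader might infer that unevaluated ocular events vanish from the safety results. They do not: they leave only the three AESI outputs. A reader might also infer that the lost events would be mainly the mild ones. Neither document ties referral to severity or gives a referral rate, so that is conjecture.

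**Conclusion.** The wording in SAP 9.B differs from the protocol's AESI definition, the difference is neither declared nor justified, and applied literally it would make three AESI outputs depend on whether referral took place. That much rests on the text alone.

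The size is not known and may be zero. The illustrative counts rest on rates from another drug, conjunctivitis only, the planned enrolment, and an assumed evaluation share that is equal across groups. They show how the AESI row would respond, not what this trial will find.

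This is a modest point about a descriptive safety summary. It is worth correcting because it concerns the only AESIs the protocol names.

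**What to change.** In SAP 9.B, delete the words about evaluation by an ophthalmologist and restate the definition in protocol 11.1.5: all conjunctivitis, keratitis and other ophthalmic events, whether or not a specialist evaluated them. Preferably implement it with a list of MedDRA preferred terms fixed before unblinding, so that the row, table and listing all draw on one set. The protocol does not require such a list, but it would remove the programmer's choice.

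Show ophthalmologist evaluation as a sub-row only if the CRF already captures it. The items in protocol 11.1.4 do not include it, so that sub-row cannot be assumed to be free of new data collection.

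The cost of the main change is one edited sentence and, if adopted, a term list. It needs no new data and does not alter any efficacy analysis or the general TEAE tables.
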